3.2. Study Design Rationale

3.2.1. Blinding, Control, Study Periods, Treatment Groups

Blinding and a placebo control will be used in this study since there is no established comparator therapy to prevent β -cell loss in T1D and to reduce potential bias during data collection and evaluation of clinical, safety, and exploratory endpoints.

There will be a 28-day screening period to allow for all assessments required for randomization to be conducted. The primary endpoint will occur at Week 52 (double-blind period). Due to the natural history of β -cell loss following diagnosis, documenting a statistically significant and meaningful effect of a β -cell sparing agent in a study of a reasonable size is best accomplished at Week 52 and allows for important comparisons with other recent immune intervention studies in T1D which have used a 52-week primary endpoint.^{25,26,31,52,55,57,61} Golimumab and other TNF α -blockers are usually prescribed as continual “chronic” therapies for their autoimmune indications; therefore, the 52-week treatment duration is consistent with these experiences and will allow the best opportunity for evaluating efficacy of golimumab and ensure robust and meaningful safety evaluations.^{22,32,59,68} Following the primary endpoint analysis at Week 52 (double-blind period), an off-therapy follow-up period for 52 weeks will allow for continued assessment of safety and understanding of the durability of effect after discontinuation of therapy. This will provide data to assist in developing dosing strategies of golimumab for T1D in future studies.

Randomization will be used to minimize bias in the assignment of subjects to treatment groups, to increase the likelihood that known and unknown subject attributes (eg, demographic and baseline characteristics and disease severity) are evenly balanced across treatment groups, and to enhance the validity of statistical comparisons across treatment groups.

Per inclusion criteria, all randomized subjects will have a C-peptide level of ≥ 0.2 pmol/mL from a 4-hour MMTT at screening. Stratification will be employed based on subjects baseline MMTT-stimulated C-peptide AUC level as previous interventional studies in new-onset T1D suggest the response to immune therapies in new-onset T1D studies may be influenced, at least in part, by subject’s baseline endogenous β -cell function.^{31,55} To achieve balanced populations in the 2 treatment groups, eligible subjects will be randomized based on 2:1 ratio to receive active study agent or placebo within each stratum (< 0.66 pmol/mL or ≥ 0.66 pmol/mL). This stratification threshold of 0.66 pmol/mL was chosen based on simulations and calculations derived from existing data that this level is expected to be close to the median of the baseline MMTT-stimulated 4-hour C-peptide AUC of the study population.^{27,60}

Following database lock for the double-blind treatment period (Week 52), subjects who are still in the off-therapy follow-up period (Week 52 to 104 visits), who were on active drug during the double-blind period and who meet the response criteria will be offered the option to participate in the open-label extension period if eligibility criteria are met. Prior to initiating open-label screening assessments, subjects and parents/legal guardians will sign updated informed consent form (ICF)/assent forms.

Subjects who did not meet the response criteria at Week 52 will continue the off-therapy follow-up period.

Subjects who met the response criteria but either declined to participate in the open-label extension period, or were determined to be on placebo, will continue the off-therapy follow-up period as planned.

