2. OBJECTIVES, ENDPOINTS, AND HYPOTHESIS

2.1. Objectives and Endpoints

- Double-Blind Period

Objectives	Endpoints
Primary Objective and Endpoints	

 • To determine if golimumab can preserve β-cell function in children and young adults with newly diagnosed T1D. 	
 • The Mixed-meal Tolerance Test (MMTT) - stimulated 4-hour C-peptide area under the concentration-time curve (AUC) at Week 52.
Secondary Objectives and Endpoints: Efficacy	

 • To evaluate the impact of golimumab on measures of diabetes control in this subject population. • To evaluate the off-therapy durability of golimumab on measures of diabetes control in this subject population. 	
 • Change from baseline in insulin use in units per kilogram body weight per day over time. • Change from baseline in HbA1c over time. • Hypoglycemic event rates (defined as BG of ≤ 70, 55, and 35 mg/dL or clinical sequelae in the absence of a BG reading) through Week 52, after Week 52 through Week 104, and the entire study. • MMTT-stimulated 4-hour C-peptide AUC over time.

Objectives	Endpoints
Secondary Objective and Endpoints: Safety	

 To determine the safety and tolerability of golimumab in children and young adults with T1D. 	
 Proportion of participants with treatment-emergent AEs and severe AEs through Weeks 52 and 104. Proportion of participants with severe infections through Weeks 52 and 104. Proportion of participants with study agent injection site reactions through Week 52.
Secondary Objective and Endpoints: Pharmacokinetics (PK) and Immunogenicity	

 To evaluate the PK and immunogenicity of golimumab in this specific subject population with T1D. 	
 Summary of serum golimumab concentrations and the PK profile after induction and maintenance dosing. Incidence and titers of antibodies to golimumab.
Exploratory Objective and Endpoints: Immunologic and Metabolic	

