11.2. Sample Size Determination

The sample size calculation is based on the primary endpoint, an MMTT 4-hour C-peptide AUC at Week 52. Due to skewed C-peptide AUC data, normalizing transformation of $\log(AUC + 1)$ is applied for sample size assessment. The method has been well accepted and used in numerous clinical studies^{25,26,42,57,60}. Based on published data, a common SD of $\log(AUC + 1)$ of 0.215 is assumed, and the back-transformed means for 4-hour C-peptide AUC are assumed to be 0.385 and 0.635 for the placebo and golimumab groups respectively, ie the expected treatment difference (back-transformed) is 0.25. With 81 subjects (54 on golimumab and 27 on placebo) and an alpha of 0.05 (2-sided), there is 90% power to detect the treatment difference through a 2-sample t-test.

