5.2.2.1. Missing Data

Unless otherwise specified, in situations with the presence of missing data (e.g. lost to follow-up, missed study visit) the following rules will apply:

Missing baseline value: No imputation will be performed for missing baseline values.

Subjects missing values for any subgroup parameters (defined in Section 2.4) at baseline will be excluded from the subgroup analysis.

Continuous endpoints:

- In general, no imputation will be performed for missing post-baseline continuous values. Missing data will be adjusted for in the statistical model (i.e. Mixed effect Model Repeated Measures)
- In several sensitivity analyses of the primary endpoint, missing C-peptide AUC value will be imputed through linear extrapolation. More specifically, missing $\log(\text{AUC}+1)$ value will be imputed through a random effect model with time (continuous), age, treatment, and treatment by time interaction as fixed effects, and intercept and slope at subject level as random factors.
- Multiple Imputation (MI) is applied in one sensitivity analysis of the primary endpoint.

Binary endpoints:

- In general, subjects with missing observations of interest at a visit will be regarded as non-responders for that visit.
- When evaluating sustained response status for C-peptide AUC, if a subject presents one or more intermittent missing C-peptide AUC value, then the response statuses at visits prior to and after the miss value(s) will be referred to. If the subject is a responder at both visits, the he/she will be regarded as a responder at the missing visit. If the subject is a responder at the visit prior to the missing value and a non-responder at the visit after missing value(s), then the subject becomes a non-responder at the first missing visit. If all C-peptide AUC values after a visit are missing, then the response status for those missing visits is set to be non-responder.

Time-to endpoints:

- For time-to peak C-peptide < 0.2 pmol/mL, in case of intermittent missing measurement, if both the previous value and the next observed value are ≤ 0.2 , then the missing value is regarded as ≤ 0.2 . Otherwise, treat the first missing value above 0.2.
- Similarly, for time-to loss of remission (remission duration), in case of intermittent missing measurement, if both the previous and the next observed value are ≤ 9 (in remission), then the missing value is regarded to be ≤ 9 . Otherwise, treat the first missing value above 9.

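### Only golimumab-arm responders may leave off-therapy follow-up, nothing says how the durability comparison treats them, and the stated default rules would bias Week 104 against golimumab

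*Protocol*

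**What the plan says.** Protocol 3.2.1 limits the extension to subjects "who were on active drug during the double-blind period and who meet the response criteria will be offered the option to participate". Everyone else stays: "Subjects who did not meet the response criteria at Week 52 will continue the off-therapy follow-up period", and responders who declined, "or were determined to be on placebo, will continue the off-therapy follow-up period as planned". Response is defined in Protocol 3.1 from the change in C-peptide AUC and the insulin-dose-adjusted HbA1c score (IDAA1c), both at Week 52. The offer follows the first database lock, which waits until every subject has finished Week 52.

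Protocol 2.1 keeps this secondary objective: "To evaluate the off-therapy durability of golimumab on measures of diabetes control in this subject population". Its endpoints include C-peptide AUC, HbA1c and insulin use over time, with visits at Weeks 78 and 104.

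On analysis:
- Protocol 11.3 writes the MMRM for the Week 52 endpoints, and 11.3.1 adds only descriptive extension analyses.
- The SAP introduction restricts the SAP to the Week 52 lock. SAP 1.2 lists two locks and does not mention the extension.
- SAP 2.1 uses nominal visits.
- SAP 5.5.2 gives by-arm summaries, and an MMRM for selected continuous endpoints where judged sensible.
- SAP 5.2.2.1 says of binary endpoints that "subjects with missing observations of interest at a visit will be regarded as non-responders for that visit". For continuous endpoints it imputes nothing and relies on the MMRM.

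**The concern.** The golimumab arm can lose the subjects whose C-peptide or IDAA1c held up best, and the placebo arm loses none of their counterparts. A by-arm summary of whoever is still off therapy then compares a depleted golimumab arm with an intact placebo arm. The non-responder rule is harsher: a subject who left because of a response would be scored as a failure at Week 104. At stake is the durability answer, which Protocol 3.2.1 says will help shape dosing strategies in later studies. An analysis chosen only after the data are seen would also be open to challenge.

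**Working it through.** **Inputs from the documents.** Protocol 11.2 gives an SD of 0.215 for log(AUC+1). The Week 52 means "are assumed to be 0.385 and 0.635 for the placebo and golimumab groups respectively". "With 81 subjects (54 on golimumab and 27 on placebo) and an alpha of 0.05 (2-sided), there is 90% power". Protocol 3.2.1 expects a median baseline AUC near 0.66. C-peptide response means an AUC of at least 95% of baseline.

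**Inputs assumed, because the documents give none.** Uptake among golimumab responders 25% to 100%; Week 52-to-104 correlation 0.6 to 0.9; baseline SD 0.15 to 0.215; baseline-to-Week 52 correlation 0.5 to 0.7.

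**1. The plan's own figure.** Difference = ln(1.635/1.385) = 0.166. SE = 0.215 × √(1/54 + 1/27) = 0.0507. Ratio = 3.27. A noncentral t with 79 df gives 89.9% power, so the stated 90% is reproduced.

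**2. How many could leave, and an outer bound.** With every baseline set to 0.66, the response threshold is 0.95 × 0.66 = 0.627, or 0.487 on the log scale.
- Golimumab mean ln(1.635) = 0.492, z = −0.023, so 51% respond (about 27 of 54).
- Placebo mean ln(1.385) = 0.326, z = 0.749, so 23% respond.
- If all golimumab responders left and values then stayed put, the remaining golimumab mean would be 0.492 − 0.215 × 0.399/0.491 = 0.317. Back-transformed this is 0.373, against 0.385 on placebo.

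**3. Simulation.** 1,500 trials per scenario, 54 vs 27, true Week 104 difference held at 0.166, golimumab C-peptide responders leaving at the assumed uptake. Full-data power is about 90%.

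| Uptake | Difference among those remaining | Power |
|---|---|---|
| 25% | 0.149–0.160 | 80–86% |
| 50% | 0.128–0.152 | 67–80% |
| 75% | 0.098–0.137 | 43–69% |
| 100% | 0.049–0.118 | 15–51% |

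**4. A second model.** Random intercept SD 0.17, slope SD 0.12 per year, residual SD 0.06, baseline mean 0.55. About 40% of the golimumab arm qualifies.
- Individual slopes stop at Week 52: Week 104 SD = √(0.17² + 0.12² + 0.06²) = 0.217, close to the design. The remaining difference is about 0.141 at 50% uptake and 0.099 at 100%.
- Slopes run on off therapy: SD = √(0.17² + 4 × 0.12² + 0.06²) = 0.300, well above 0.215. The figures are about 0.116 and 0.035, a pessimistic limit.

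Together, steps 3 and 4 give about 0.12 to 0.15 at 50% uptake and 0.03 to 0.12 at 100%.

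**5. Non-responder coding.** Same second model, with both arms assumed to fall a further 0.10 on the log scale off therapy. If slopes stop, a true gap of about 15 points becomes about 7 at 50% uptake and −1 at 100%. If they run on, about 18 points becomes 5 and then −8.

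**6. Keeping everyone.** In the step 3 scenarios, a regression-based estimate conditioning on baseline and Week 52 AUC returns 0.164 to 0.167. Its SE rises from about 0.050 to 0.053–0.064 at full uptake.

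**7. Timing.** Assume uniform accrual over A = 52 or 78 weeks (Protocol 3.1 expects 12 to 18 months) and an offer L = 0 to 16 weeks after the last Week 52 visit. The share not yet at Week 78 is (26 − L)/A, from 10/78 = 13% to 26/52 = 50%. The share not yet at Week 104 is (52 − L)/A, from 36/78 = 46% to 52/52 = 100%.

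**The case against.** The strongest reply is that no text commits to comparing only those who remain. The SAP stops at the Week 52 lock, no Week 104 SAP is among the documents, and SAP 5.2.2.1 points to an MMRM for missing continuous data. Protocol 11.3 and SAP 5.4.2.1 already assign an MMRM to HbA1c and insulin use. A reader might infer that the amendment has itself biased the durability result, or that a real effect will be erased. The documents support neither reading: the analysis is left open, an all-subject likelihood analysis removes most of the bias, and near-complete loss of a fully maintained effect needs near-complete uptake.

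Timing and eligibility also limit the problem. At most about half of subjects could still be short of Week 78 when offers start, and entrants must meet the MMTT criteria again and most entry criteria. Protocol 9.1.2.1 and 9.1.4 also say that extension screening must fall in the 14 days before Week 104. Read literally, that leaves little off-therapy time unobserved; it may instead be meant as a latest date. The passages should be reconciled.

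These points narrow the size. They do not close the gap: the existing MMRM text targets Week 52, its use for C-peptide AUC over time is discretionary, and no rule covers data after restart.

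**Conclusion.** The concern holds as a conditional one. Departure is one-sided and depends on the outcome, the durability analysis does not address it, and the default summaries and binary rule would bias Week 104 against golimumab if applied there. The bias among remaining subjects is about 0.01 to 0.05 of a true 0.166 at 50% uptake and about 0.05 to 0.13 at 100%. Full uptake before Week 104 is an outer case given the timing in step 7. Week 78 is affected less, and the Week 52 primary analysis not at all.

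The sizes rest on assumed uptake, correlations and slopes. They count C-peptide responders only and omit remission-score responders and the IDAA1c limit. The good recovery in step 6 assumes that departure depends only on AUC values in the model. Real departure also depends on IDAA1c and the later screening MMTT. At full uptake the model must extrapolate, since no golimumab C-peptide responder is then observed off therapy.

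**What to change.** Before the Week 104 lock, state in the Week 104 SAP that:
- Week 78 and 104 comparisons of C-peptide AUC, HbA1c and insulin use extend the MMRM used at Week 52 to all mITT subjects and all visits from baseline to Week 104. Its use is fixed, not discretionary. Values after open-label restart are set to missing, so the target is the off-therapy difference had nobody restarted.
- The extension-screening MMTT taken before restart counts as an off-therapy value. A nominal-visit model with unstructured covariance has no place for it, so either map it to Week 78 or 104 by a stated window, or use the continuous-time random-effects model of SAP sensitivity analysis 2.
- For binary endpoints, extension entrants are multiply imputed from that model and not coded as non-responders.
- A sensitivity analysis covers departure that depends on IDAA1c and the screening MMTT, for example by adding both to the imputation model.
- Observed-case summaries are labelled as depleted of golimumab responders.

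The cost is SAP wording, a little more analysis and a somewhat wider Week 104 interval (the SE change in step 6). No new data are needed.

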3.2.2. Dose Rationale

This study uses a dosing regimen designed specifically for T1D. It is accepted that different diseases may require unique dosing approaches of the same therapeutic to be most efficacious. In the case of the class of TNF α -blockers, there are a variety of dosing regimens that are disease-specific such as a higher dose regimen of SC golimumab for the treatment of UC as compared to that for rheumatic diseases.

The choice of dose and regimen for this study is based upon 3 factors: 1) disease-specific considerations of T1D, 2) modeling based upon the reported efficacy of TNF α inhibition of etanercept in a pilot study in children with T1D, and 3) the sponsor's safety and pharmacokinetic (PK) the experience with golimumab in adults, adolescents and children.⁴⁸ Although, the dose regimen of SC golimumab chosen for the present T1D study has not been studied before, the sponsor's use of golimumab in adult and pediatric subjects with other indications indicate that the overall exposures in this study population are overlapping with previous experience and thus the existing safety profile of golimumab is applicable to this study.

1. T1D Disease-Specific Considerations

In T1D, the destruction of β -cells is rapid at the time of diagnosis and is considered irreversible.^{6,69,73} For aggressive immune-mediated diseases, higher and/or more frequent induction doses of anti-inflammatory therapies followed by lower regular maintenance doses are often used to gain rapid control of rampant disease activity, and then keep it under control. For most autoimmune indications, including pediatric and adult UC and CD, psoriasis, and in some cases RA, TNF α -blockers are administered using an induction regimen followed by maintenance treatment dosing regimen^{14,22,32,59,68} To preserve residual β -cells in newly diagnosed T1D, rapid neutralization of the inflammatory, anti- β -cell response is likely to be key for an effective therapy. Golimumab steady-state concentrations are only achieved after at least 3 months with routine dosing, and with such a regimen continued β -cell destruction may likely occur. It was determined that 2 SC induction doses spaced by 2 weeks would more rapidly achieve a steady-state level and giving the best opportunity to protect residual β -cells. The induction doses will be followed by a lower maintenance dosing in order to maintain steady-state concentrations and continue to prevent further β -cell loss.

2. Model-Based Prediction of TNF α Suppression in T1D Subjects

To date golimumab has been studied in 2 pediatric populations; pJIA and pediatric UC. In the study of golimumab in children 2 to 18 years old with pJIA who were being treated with concomitant methotrexate (MTX) the dose was 30 mg/m² SC every 4 weeks (q4w). In the study of golimumab in children 6 to 18 years old with pediatric UC that dose was 90 mg/m² SC at Week 0 and 45 mg/m² SC at Week 2, and 45 mg/m² SC q4w for children <45 kg and 200 mg SC at Week 0 and 100 mg SC at Week 2, and 100 mg SC q4w in children \geq 45 kg. The approved dose of golimumab in adults (those 18 years old and above) with RA, PsA, and AS is 50 mg SC q4w and for UC is 200 mg SC at Week 0, followed by 100 mg SC at Week 2 and then 100 mg SC q4w.

A mechanistic PK/target engagement (TE) model incorporated PK exposure from a previously established population PK model-based on the pJIA population was paired with a target-mediated drug disposition model to assess the interaction between drug and target and to simulate the suppression of TNF α after TNF α -blocker administration. The PK/TE model was developed based on the assumption that the etanercept dosing regimen tested in T1D results in sufficient TNF α neutralization given the positive results observed in the pilot trial in children with new-onset T1D.⁴⁸ The golimumab dosing regimen was designed to approximate the extent of TNF α suppression obtained using the etanercept dosing regimen in this study and accounting for the differences in PK and TNF α binding affinity between golimumab and etanercept. Concomitant use of MTX, which is standard of care in pJIA, reduces golimumab clearance in subjects with this disease, likely due to suppression of anti-drug antibodies.⁷⁷ Subjects with T1D do not receive MTX, therefore, a 56% faster clearance of golimumab in subjects with T1D than pJIA subjects was assumed for predicting the PK profile in the T1D population.

[figure not shown]
The PK/TE model suggested that an induction dosing regimen of 60 mg/m² SC (to a maximum of 100 mg) at Week 0 and Week 2 followed by a maintenance dosing regimen of 30 mg/m² SC (to a maximum of 50 mg) q2w or 60 mg/m² SC (to a maximum of 100 mg) q4w results in suppression of TNF α to a level approximating that of etanercept. This target would not be achieved with a 30 mg/m² SC q4w dose. The 30 mg/m² q2w and 60 mg/m² q4w maintenance dosing regimens would have the same overall exposure (AUC) and similar TNF α suppression; however, the 60 mg/m² q4w regimen would have higher peak/trough concentration fluctuations and thus more fluctuation on suppression of TNF α . It is known that TNF α has direct cytostatic and cytotoxic effects on β -cells.^{2,58} Thus the TNF α elevations that would be expected to occur during the troughs with the higher, but less frequent dosing, may result in more damage to residual β -cells. As the overall exposure to golimumab with these dosing regimens may be considered equivalent, the 30 mg/m² SC (to a maximum of 50 mg) q2w dosing regimens was preferred due to less peak/trough fluctuation.

3. Comparison of Golimumab Dose Regimens Between the T1D Population with Other Disease Populations of Adults and Children

Population PK simulations were performed comparing the proposed T1D dosing regimen with dosing regimens that have previously been studied in the pediatric populations (pJIA and pediatric UC, [Figure 3](#) Panels A and B, respectively). The simulations to develop this dosing

strategy used demographics for subjects age 6 through 21 years based upon the U.S. Centers for Disease Control and Prevention growth charts.¹⁸ For a child, golimumab 30 mg/m² (50 mg/1.67 m²) would be approximately equivalent to a 50 mg dose for an adult subject weighing 60 kg (with a body surface area [BSA] of 1.67 m²). Thus the 30 mg/m² dose is expected to be similar to the 50 mg dose in adults and the 60 mg/m² dose to be similar to the 100 mg dose in adults. In adults, golimumab 50 mg q4w was the minimum effective dosing regimen for the treatment of RA, PsA, or AS. Due to the absence of concomitant MTX in T1D subjects, it is expected that a 30 mg/m² q4w dosing regimen that is the pediatric equivalent to the adult 50 mg q4w dose may not result in sufficient systemic exposure for suppressing TNF α in T1D subjects, therefore a higher dose or more frequent dosing interval should be studied. For the simulation, a 40 kg weight cut-off was included (Figure 3 Panel A: <40 kg: 30 mg/m² q4w; \geq 40 kg: 50 mg q4w). For the pediatric UC simulations, a 45 kg weight cut-off was implemented as previously studied, such that subjects <45 kg would receive 60 mg/m² at Weeks 0 and 2 followed by 30 mg/m² q2w and subjects \geq 45 kg would receive 100 mg at Week 0 and 2 followed by 50 mg q2w. Based on the PK simulations, the proposed T1D dosing regimens (<45 kg and \geq 45 kg) are expected to result in drug exposure (AUC) between that observed for the pJIA with MTX and pediatric UC populations without MTX (Figure 3, Panel A and B), although the 30 mg/m² q2w maintenance dosing interval will produce slightly higher trough concentrations.

Figure 3: Overlap of simulated golimumab exposure for dosing regimens in current T1D study compared to those in pJIA and pediatric UC studies.

The safety and efficacy of golimumab has been extensively characterized in adult subjects with RA, PsA, AS, and UC. In a Phase 2 study in subjects with RA, 4 different dosing regimens were

evaluated (50 mg q2w or q4w and 100 mg q2w or q4w) of which all doses tested were generally well tolerated and effective in maintaining clinical response without dose-related safety events through Week 52.³⁵ In pJIA, a 30 mg/m² q4w dosing regimen was studied up to a maximum of 50 mg (the approved adult RA dose). In pediatric UC, a 45 kg weight cut-off was implemented such that subjects below 45 kg received BSA-adjusted doses and subjects at or above 45 kg received doses according to adult UC dosing regimens (details discussed above). To date, the dosing regimens studied in pediatric patients were well tolerated. Overall no new adverse drug reactions were identified. Further, the frequency, type, and severities of the events observed were similar to those observed in the adult rheumatology and inflammatory bowel disease studies. Since the dosing regimen for golimumab proposed for this study in T1D subjects is expected to result in drug exposures that overlap with those observed in previous pediatric studies with golimumab, it is appropriate to also expect that a similar safety profile will be demonstrated in the T1D population planned for enrollment in this trial as that seen in pediatric studies in pJIA and UC.

Considering the above-mentioned disease-specific issues of T1D, pharmacologic comparisons of golimumab and etanercept and specific experience with golimumab, an induction dosing regimen of 60 mg/m² SC (to a maximum of 100 mg) at Weeks 0 and 2, followed by a maintenance dosing regimen with 30 mg/m² SC (to a maximum of 50 mg) q2w was selected as the recommended dosing regimen in this study. In addition, a weight cut-off (45 kg), which has been implemented in the clinical pediatric UC study of golimumab, will also be studied such that subjects at or over the 45 kg weight cut-off will receive golimumab using the already approved adult PFS-U presentations.

